8.6.2 Subjective Global Assessment

8.6.2.1 Proportion of Patients that Report Adequate Relief of CS Symptoms at Each Study Visit

At each study visit, patients will be asked to respond to the following question: “In the past 7 days, have you had adequate relief of your carcinoid syndrome bowel complaints such as diarrhea, urgent need to have a bowel movement, abdominal pain, or discomfort?” Patients are regarded as reporting adequate relief of CS symptoms during the previous week if the result to the question answered is “yes”.

The number of patients that report adequate relief of CS symptoms and its percentage along with the corresponding exact 95% CIs will be summarized by study visit.

Generalized linear mixed model can be used to fit the binary response with repeated measurements. The odds ratio of each telotristat etiprate group versus its Baseline, its associated 95% CI and p-value will be reported for each post-Baseline visit. A sample SAS code for the model is shown below:

```
*USUBJID: unique patient ID  
AVISITN: analysis visit (eg, week 12, 24, 36, 48, 60, 72, 84 and Follow-up)  
RESP: binary response data (eg, ‘Yes’ for adequate relief of CS symptoms)  
BASE: Baseline response;  
  
proc glimmix data=adef;  
class USUBJID AVISITN PLA5HIAA;  
model RESP = AVISITN BASE /  
solution dist=binomial link=logit ddfm=kr oddsratio;  
random intercept / subject=USUBJID ;  
random AVISITN / subject=USUBJID type=ARH(1);  
run;
```

A graph of the percentage of patients that report adequate relief of CS symptoms by study visit and treatment group will be plotted.

1003157

Lexicon Pharmaceuticals, Inc.

LX1606.302

Final V1.0

Statistical Analysis Plan

8.6.2.2 Change from Baseline in subjective global assessment of CS symptoms on an 11-point NRS at each study visit

Patients will be asked the following question at each study visit to assess global symptoms associated with CS on an 11-point scale: “Rate the severity of your overall carcinoid syndrome symptoms over the past 7 days on a scale from 0-10, where 0=no symptoms and 10 = worst symptoms ever experienced.”

Analysis of this endpoint is similar to that applied in [Section 8.6.1 Change from Baseline in Overall and Domain Scores of the EORTC QLQ-C30 and GI.NET21 at Each Study Visit](#). A graphic display of the change from Baseline value and its 95% CLs over time for each treatment group will be provided.

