8.6.3 Change from Baseline in Plasma Levels of 5-HIAA at Each Study Visit

Fasting (of at least 6 hours) blood samples, for measurement of 5-HIAA in plasma, will be collected and analyzed by a specialty laboratory based on the scheduled of visits in [Table 1](#).

The change from Baseline in plasma 5-HIAA levels will be analyzed using a MMRM. The model will use the change from Baseline in plasma 5-HIAA levels as the dependent variable, and will include patient as a random effect, Baseline plasma 5-HIAA levels as a covariate, time as fixed effect. The Kenward-Roger approximation will be used to adjust the denominator degrees of freedom. A first-order heterogeneous autoregressive covariance structure will be assumed initially to model the within-patient errors; however, other covariance structures will be tested and may be used in the final model if a better fit is evident. The LS means, a 95% 2-sided CLs and the p-values of LS means at each visit will be reported for each study visit to evaluate the treatment effect. A sample SAS code for the model is shown below.

*USUBJID: unique patient ID
AVISITN: analysis visit (eg, week 12, 24, 36, 48, 60, 72, 84 and follow-up visit)
PLA5HIAA: Baseline plasma 5-HIAA levels
RESP: non-count data (eg, change from Baseline in plasma 5-HIAA level)

```
ods output lsmeans=estimates;  
proc mixed data=adev method=reml;  
  class USUBJID AVISITN;  
  model RESP = PLA5HIAA AVISITN / ddfm=kr;  
  repeated AVISITN / subject=USUBJID type=ARH(1);  
  random intercept / subject=USUBJID;  
  lsmeans TRT01PN*AVISITN / cl;  
run;  
ods output close;
```

Lexicon Pharmaceuticals, Inc.
[name]
[name]

1003157

Lexicon Pharmaceuticals, Inc.

LX1606.302

Final V1.0

Statistical Analysis Plan

Descriptive summary statistics will be provided for the observed value and change from Baseline value of the plasma 5-HIAA levels. A graphic display of the parameter estimates and the 95% CLs for the plasma 5-HIAA levels over time will be provided.

Friedman's test for repeated measures will be used to supplement the MMRM, which is similar to that applied in Section **Error! Reference source not found.****Error! Reference source not found.**

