As discussed, please prevent race information for patient [REDACTED], as well as any other subjects from [REDACTED] from being displayed in any tables or listings for any interim or final study report for LX1606.302.

Thank you.

[REDACTED]

[REDACTED], MD
[REDACTED], Clinical Operations
Lexicon Pharmaceuticals

Lexicon Pharmaceuticals, Inc.
[name]
[name]

[name]
[contact]

MEMORANDUM

To: [REDACTED]

From: [REDACTED] MD

CC: TMF for LX1606.302, [REDACTED]

RE: Baseline Data for 302

Date: November 30, 2015

Dear [REDACTED],

As discussed, for any Study LX1606.302 patients missing baseline PPD Laboratory or Frontage (Plasma 5-HIAA) data, please link the Week 48/EOS visit in studies LX1606.301 or LX1606.303 to the Day 1 Visit in Study LX1606.302 in order for us to have complete data set.

Thank you

[REDACTED]
[REDACTED] MD
[REDACTED] Clinical Operations
Lexicon Pharmaceuticals

Note to File

Study Number: LX1606.302

Regarding: Subject Numbers from Phase II Studies

Summary of Situation:

Seven participants completed the LX1606.202 and LX1606.203 Phase II studies and enrolled in the LX1606.302 Phase III extension study. These participants retained their Subject Number from the Phase II study when entering the Phase III study. The table below describes the Subject Numbers and the Investigative site at which they participated in the Phase II and Phase III studies.

Subject Number	Site Name	LX1606.302 Site Number	Investigator Name
[REDACTED]	[REDACTED]	[REDACTED]	[REDACTED]
[REDACTED]	[REDACTED]	[REDACTED]	[REDACTED]
[REDACTED]	[REDACTED]	[REDACTED]	[REDACTED]
[REDACTED]	[REDACTED]	[REDACTED]	[REDACTED]
[REDACTED]	[REDACTED]	[REDACTED]	[REDACTED]
[REDACTED]	[REDACTED]	[REDACTED]	[REDACTED]

[REDACTED]
[REDACTED], Clinical Operations
Lexicon Pharmaceuticals Inc.

[REDACTED]
Date

NOTE TO FILE

To: LX1606-1.301-CS Trial Master File (TMF)
LX1606-1.302-CS Trial Master File (TMF)
LX1606-1.303-CS Trial Master File (TMF)

From: [REDACTED] of Biostatistics and Data Management
[REDACTED] of Biostatistics

Re: Studies LX1606-1.301-CS, LX1606-1.302-CS, and LX1606-1.303-CS (or Studies 301, 302, and 303, for short) – Correcting the Error in the Statistical Analysis Plans (SAPs) Regarding the Scoring Algorithm for the GI.NET21 Scales and Single Items

Date: February 5, 2016

I. **Incident/Finding(s)**

The following incorrect sentence appears in the SAPs for Studies 301, 302, 303:

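### The sample GLIMMIX code for adequate relief (SAP 8.6.2.1) carries a stray CLASS variable, Baseline plasma 5-HIAA, that could exclude patients for a reason unrelated to the endpoint

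*SAP*

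**What the plan says.** SAP 8.6.2.1 proposes a generalized linear mixed model for the yes/no adequate-relief answer and introduces the code with "A sample SAS code for the model is shown below".

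- CLASS statement: "class USUBJID AVISITN PLA5HIAA".
- Fixed effects: "model RESP = AVISITN BASE", with the block's legend giving "BASE: Baseline response".
- Random effects: a patient intercept, and "random AVISITN / subject=USUBJID type=ARH(1").

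The legend of this block does not mention PLA5HIAA. The variable is explained only in 8.6.3, as "PLA5HIAA: Baseline plasma 5-HIAA levels". There it is a continuous covariate in "model RESP = PLA5HIAA AVISITN / ddfm=kr" and is not in CLASS.

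Three other places bear on the point. SAP 7.2.1 takes Baseline from Day 1 of this study, and SAP 7.3 rules out imputation. The memo of 30 November 2015, appended to the SAP, deals with patients "missing baseline PPD Laboratory or Frontage (Plasma 5-HIAA) data" by linking the Week 48/EOS visit of Study 301 or 303 to Day 1. A separate note to file records seven entrants from the Phase 2 studies 202 and 203, for whom no such link is given.

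**The concern.** By default, SAS modelling procedures discard a record when any CLASS variable is missing, even if that variable is in no effect. PLA5HIAA is a patient-level value, so one missing Baseline sample would remove all of that patient's visits from the adequate-relief model. Whether a patient counts in a bowel-symptom analysis would then depend on a blood result that the analysis does not use. SAP 8.6 promises an analysis of observed data, and this line could discard answers that were observed. The modelled odds ratios would also lose patients who still count in the visit percentages reported beside them.

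Missing values are a realistic prospect. Nothing is imputed, Baseline is tied to Day 1, and the sponsor saw a need to direct how gaps in Baseline laboratory and 5-HIAA data should be handled.

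**Working it through.** The SAP gives no sample size, power or patient count for this analysis, so there is no figure to reproduce. The check compares the code statements and then bounds the loss.

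**1. Role of each variable**

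| Variable | 8.6.2.1 CLASS | 8.6.2.1 MODEL or RANDOM | 8.6.2.1 legend | 8.6.3 |
|---|---|---|---|---|
| USUBJID | yes | yes (subject) | yes | CLASS, subject |
| AVISITN | yes | yes | yes | CLASS, fixed effect |
| BASE | no | yes (fixed effect) | yes | not used |
| PLA5HIAA | yes | no | no | continuous covariate, not in CLASS |

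PLA5HIAA is the only variable in the adequate-relief CLASS statement that the model does not use. No later note to file corrects it.

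**2. What the printed code would do**

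- Dataset carries PLA5HIAA and all values are present: the extra CLASS variable has no effect on the fit.
- Dataset carries PLA5HIAA and some values are missing: all records of those patients are dropped.
- Dataset does not carry PLA5HIAA: the step stops with an error. This is possible, because 8.6.2.1 reads a dataset called adef and 8.6.3 reads one called adev.

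**3. Size of the loss**

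Inputs: up to 100 patients expected (SAP 4.5); seven Phase 2 entrants (note to file); m patients without a Baseline 5-HIAA value (not given, so assumed). If each patient carries equal information, the standard error grows by the factor √(100/(100 − m)).

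| m (assumed) | Patients left | SE factor | Increase |
|---|---|---|---|
| 1 | 99 | √(100/99) = 1.005 | 0.5% |
| 3 | 97 | √(100/97) = 1.015 | 1.5% |
| 7 | 93 | √(100/93) = 1.037 | 3.7% |
| 10 | 90 | √(100/90) = 1.054 | 5.4% |
| 20 | 80 | √(100/80) = 1.118 | 11.8% |

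If the memo's link fills every gap for patients from Studies 301 and 303, m cannot exceed 7, and 7/100 = 7%. The last two rows apply only if gaps in those patients stay unfilled.

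**4. Does leaving BASE out of CLASS matter?**

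A logistic model without random effects was fitted to simulated data (100 patients, seven visits) with a 0/1 BASE, once as numeric and once as categorical. The log-likelihood was −463.597 both times, so for a 0/1 BASE the choice makes no difference. A character BASE that is not in CLASS would stop the step. The legend gives 'Yes' as an example value of RESP but does not say how BASE is stored.

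**The case against.** The strongest reply is that this is sample code. The section says only that such a model can be used, and SAP 15 places the real programs under quality control. Other printed blocks clearly are not production code: those in 8.6.1 and 8.6.3 request least squares means for TRT01PN by visit, although TRT01PN is in neither CLASS nor MODEL. Nothing shows that the adequate-relief line was ever run. This stands, and it makes any loss conditional. It does not make the line right. The note to file of 5 February 2016 also shows that another error in this SAP, the GI.NET21 scoring rule, did reach finalised output.

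Stronger readings are tempting, but the documents do not support them:

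- A reader might infer that patients are deleted silently. Deletion requires the line to be run, the variable to be on the dataset and values still to be missing. GLIMMIX also reports observations read and used.
- A reader might infer that the Baseline response was left out of the model. It is in the MODEL statement; only its place in CLASS is open.
- A reader might take the memo as proof that patients lacked Baseline 5-HIAA. Its wording is conditional and covers two laboratories, and it gives no count.
- A reader might assume a loss of 10 to 20%. That exceeds the 7 of 100 that remain exposed if the link works as intended.

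It is also fair to say that the model and the visit percentages can rest on different patients even after correction, because the model needs a Baseline answer and the percentages do not. And this is one efficacy endpoint in an open-label extension whose primary objective is safety, with observed percentages and exact intervals reported in any case.

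**Conclusion.** The code as printed is wrong: PLA5HIAA has no function in the adequate-relief model and should not be in its CLASS statement. The consequence is conditional. It ranges from none (all values present), through the loss of every record of patients without a Baseline 5-HIAA value, to a step that does not run.

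The number affected cannot be taken from the documents. With every 301/303 gap filled, the ceiling is seven of a planned 100 patients and a standard error about 3.7% larger, and that requires all seven Phase 2 entrants to lack a sample that the schedule of events places at Day 1. For output made before the memo, such as the Draft 1 tables from the 16 October 2015 extraction, that ceiling does not apply and the number is unknown. These figures assume 100 patients and equal information per patient. The point is a correction worth making, not evidence that reported results are wrong.

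**What to change.** 1. Remove PLA5HIAA from the CLASS statement in 8.6.2.1.
2. State how BASE is stored. If it is character, use `class USUBJID AVISITN BASE;`. If it is coded 0/1, `class USUBJID AVISITN;` is enough.
3. Require the number of patients used by the model to equal the number in the analysed population with a Baseline answer and at least one post-Baseline answer, and explain any difference.
4. Check the production program. Rerun the adequate-relief model output only if that program used this CLASS line.

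The cost is a one-word change to the sample code, one reconciliation of counts and a look at one program. A short note to file would do, and a rerun is needed only if the check in step 4 finds the line in use.

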7 GENERAL ASPECTS FOR STATISTICAL ANALYSIS

7.1 GENERAL METHODS

Statistical methodology and analyses are in accordance with the principles outlined by the International Conference on Harmonisation (ICH) E9 guidelines^[1].

Patient listings of all data represented in the electronic case report form (eCRF) will be provided. Measurements from patients excluded from the predefined analysis populations or extra measurements (such as unscheduled or repeat assessments) will not be included in summary tables unless specified otherwise, but will be included in the patient listings. In general, the patient listings will be sorted by treatment group,

1003157

Lexicon Pharmaceuticals, Inc.

LX1606.302

Final V1.0

Statistical Analysis Plan

patient number, and assessment date (and time), if applicable. For most summary statistics, data will be analyzed and displayed by the order of the treatment groups and overall, where treatment groups correspond to how patients were dosed on Day 1 of this study.

Unless otherwise specified, continuous/quantitative variables will be summarized using descriptive statistics, which will include the number of patients with data to be summarized (n), mean, standard deviation (SD), median, minimum, and maximum. The same number of decimal places as in the raw data will be presented when reporting the minimum and maximum, 1 more decimal place than in the raw data will be presented when reporting the mean and median, and 2 more decimal places than in the raw data will be presented when reporting the SD.

All categorical/qualitative data will be presented using frequency counts and percentages. The total number of patients in the treatment group overall (N) will be used as the denominator for percentage calculations, unless stated otherwise in the table shell. All percentages will be presented as 1 decimal point, unless otherwise specified. Percentages equal to 100 will be presented as 100%, and percentages will not be presented for zero frequencies.

All statistical tests will be 2-sided and have an associated α -level = 0.05 unless mentioned otherwise. Confidence limits (CLs) will be 2-sided and calculated with a 95% confidence coefficient.

All statistical analyses will be done using SAS statistical software version 9.3 or higher.

In the case of multiple or repeat assessments at a scheduled visit, the latest value at the visit will be used for summarization and analyses.

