The change from Baseline in overall and each domain score of EORTC QLQ-C30 and GI.NET21 at each study visit will be analyzed using a MMRM for the PP population. The model will use the change from Baseline in overall or each domain score of EORTC QLQ-C30/GI.NET21 as the dependent variable and will include a fixed effect of time (Baseline Day 1 up to Week 84/EOS). The Baseline QLQ-C30/GI.NET21 value will be included in the model as a covariate. The Kenward-Roger approximation will be used to adjust the denominator degrees of freedom. A first-order heterogeneous autoregressive covariance structure will be assumed initially to model the within-patient errors; however, other covariance structures will be tested and may be used in the final model if a better fit is evident. The least squares (LS) means, 95% 2-sided CLs, and the p-values of LS means at each visit will be reported to evaluate the within-patient treatment effect. The null hypothesis is that there is no treatment effect (no difference from Baseline values) over time. A sample SAS code for the model is shown below.

*USUBJID: unique patient ID
AVISITN: analysis visit (e.g., week 24, week48, week 72 and week 84)
RESP: non-count data (e.g., change from Baseline in Global health status/QOL score)
BASE: non-count data (e.g., Baseline Global health status/QOL score);

```
ods output lsmeans=estimates;  
proc mixed data=adeft method=reml;  
  class USUBJID AVISITN;  
  model RESP = AVISITN BASE / ddfm=kr;  
  repeated AVISITN / subject=USUBJID type=ARH(1);  
  random intercept / subject=USUBJID;  
  lsmeans TRT01PN*AVISITN / cl;  
run;  
ods output close;
```

Friedman's nonparametric method for testing treatment group differences will be used to supplement the MMRM. Friedman's test uses the ranks of the data rather than their raw values to calculate the statistic, and the test does not make a distribution assumption of the data. The null hypothesis of the test is that the change from Baseline in Global health status/QOL score are the same over time, and the alternative hypothesis is that the change from Baseline in Global health status/QOL score are different over time. Friedman's test cannot handle missing data, so patients with incomplete measurements will be dropped when applying Friedman's test. A sample SAS code for the model is shown below.

*USUBJID: unique patient ID
AVISITN: analysis visit (eg, week 24, week48, week 72 and week 84)
RESP: change from Baseline in Global health status/QOL score;

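### The sample model for adequate relief adds a random effect with its own variance at every visit, which one Yes/No answer per patient-visit can hardly support, so the visit odds ratios can shift with it

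*SAP*

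**What the plan says.** SAP Section 8.6.2.1 tabulates the number and percentage of patients with adequate relief at each visit, with exact 95% intervals, and plots the percentages. It then says that a generalized linear mixed model can be used. For each post-Baseline visit, an odds ratio versus Baseline with confidence interval and p-value will be reported.

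The sample code sets out:

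- Response: "RESP: binary response data (eg, ‘Yes’ for adequate relief of CS symptoms".
- Visits: "AVISITN: analysis visit (eg, week 12, 24, 36, 48, 60, 72, 84 and Follow-up".
- Fixed effects: "model RESP = AVISITN BASE".
- Distribution and options: "solution dist=binomial link=logit ddfm=kr oddsratio".
- First random statement: "random intercept / subject=USUBJID".
- Second random statement: "random AVISITN / subject=USUBJID type=ARH(1".

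The linear models in Sections 8.6.1 and 8.6.3 place the same structure in a residual statement, "repeated AVISITN / subject=USUBJID type=ARH(1", and the text there describes it as a model for the within-patient errors. Section 7.1 reduces repeat assessments to one: "the latest value at the visit will be used for summarization and analyses". Section 7.5 uses a different selection rule, but it also leaves one record per visit. Section 4.5 expects up to 100 patients, with no formal sample size calculation.

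**The concern.** In PROC MIXED, a REPEATED statement describes the residual covariance. In PROC GLIMMIX, a RANDOM statement does so only with the RESIDUAL option. Without it, the ARH(1) line is a G-side effect on the logit scale: every patient has an intercept plus a separate random deviation at each visit, with a different variance at each visit. The purpose stated for the linear models has not carried over to the binary one.

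A single binary answer carries no direct information about its own extra variance. Raising a visit's log-odds and its variance together gives almost the same proportion. Only the association between visits and the shared baseline slope separate the two. The odds ratios and p-values that the SAP commits to reporting could therefore rest partly on variance estimates that the data do not determine. Section 8.6.2.1 states no fallback; the clause allowing other covariance structures appears in Sections 8.6.1 and 8.6.3 only.

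**Working it through.** The SAP gives no response rate, variance or effect size for this endpoint, so there is no planned figure to reproduce. Everything marked as assumed below is an input chosen for the check.

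**1. The model as coded.** For patient i at visit t:

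logit Pr(Y_it = 1 | u_i, v_it) = β_t + γ·BASE_i + u_i + v_it, with u_i ~ N(0, s²), v_it ~ N(0, σ_t²) and corr(v_it, v_ik) = ρ^|t−k|.

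The visits are Weeks 12, 24, 36, 48, 60, 72, 84 and Follow-up, so T = 8. Covariance parameters: 8 visit variances + 1 correlation + 1 intercept variance = 10. Data: at most 100 patients, one 0/1 per visit.

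For a given baseline response, the proportion at visit t depends on the random effects only through s² + σ_t². So β_t and σ_t² can rise together at an almost constant proportion.

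**2. Full likelihood, one visit.** Assumed truth: 100 patients with complete data, random intercept only, log-odds 1 at one visit and 0 at the other seven. The conditional odds ratio is exp(1) = 2.72. All 2^8 = 256 response patterns are enumerated by quadrature. An extra SD of 2 is then imposed at that visit and the other parameters are refitted. The expected likelihood-ratio chi-square is 2 × 100 × the Kullback-Leibler divergence.

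| Intercept SD (assumed) | Proportion at that visit (others 50%) | Chi-square (3.84 needed) | Refitted odds ratio | Marginal odds ratio |
|---|---|---|---|---|
| 1.0 | 69.7% | 0.95 | 4.36 | 2.30 |
| 1.5 | 67.1% | 1.81 | 3.96 | 2.04 |
| 2.0 | 64.8% | 2.37 | 3.68 | 1.84 |

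In no row would 100 patients be expected to reject the false variance at the 5% level.

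**3. Full likelihood, the whole coded model.** With the binary baseline covariate, intercept SD 1, visit SD 1 and correlation 0.5 (all assumed), the Week 84 visit SD is fixed at a wrong value and everything else is refitted. The odds ratio is Week 84 versus Week 12.

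| Assumed rates | True odds ratio | SD fixed at 0.1 | SD fixed at 2 | SD fixed at 3 |
|---|---|---|---|---|
| 70-88% | 2.46 | 1.82 (chi-square 0.21) | 4.24 (0.16) | 8.47 (0.53) |
| 47-63% | 1.65 | 1.51 (0.46) | 1.98 (0.25) | 2.47 (0.81) |

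The standard error of a log visit SD is 1.4 to 2.3 when the true SD is 1. Even at 1.4, a 95% interval for the SD runs a factor of exp(1.96 × 1.4) = 15.5 either way.

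**4. The estimator the code invokes.** There is no METHOD= option and Kenward-Roger is requested, so GLIMMIX uses its default linearised pseudo-likelihood, not full likelihood. Two small sets of simulated trials (pseudo-likelihood coded in Python, not SAS; 100 patients) compared the coded covariance with a random intercept alone:

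- Near 50% response: the log odds ratios differed by 0.02 and 0.03 root mean square in the two sets. In the second set the largest difference was 0.10, and median standard errors were 0.332 and 0.330.
- Higher response: in the first set, with rates of about 72-84%, the root mean square was 0.21 and the largest difference 0.57, a factor of exp(0.57) = 1.77. In the second, with log-odds of 1.3 and 2.5, they were 0.20 and 0.67 (exp(0.67) = 1.95); median standard errors were equal at 0.40.

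A typical shift at the higher rates is thus exp(0.21) = 1.23-fold, with single trials reaching about 1.8-fold or slightly more.

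**5. The promised contrast.** The listed visit levels are all post-Baseline and BASE is a covariate. No Baseline level exists in the code, so an odds ratio of a visit versus Baseline cannot be formed from it. The ratios in steps 2 to 4 are therefore visit against visit.

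**The case against.** Four points can be made for the plan.

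- **The endpoint does not need the model.** It is a proportion, reported directly with exact intervals and a graph. This stands, and it limits the severity.
- **The code is a sample, and the wording is permissive.** Section 8.6 also asks for a model suited to the measurement properties of the variable. That leaves room to adapt, but this is the only model given for the endpoint and its odds ratios are to be reported.
- **The default estimator behaves better than full likelihood.** A reader might infer from steps 2 and 3 that reported odds ratios would jump from 2.7 to about 4, or that arbitrary variances will drive the result. The documents do not support that: the code calls pseudo-likelihood, under which the surplus visit SDs often collapsed to zero and little changed near 50% response. What stands is that the odds ratio can move materially when rates are well away from 50%.
- **A conditional odds ratio is legitimate.** A reader might blame the ARH(1) line for the gap between 2.72 and the marginal 2.30, 2.04 or 1.84 in step 2. That gap comes entirely from the random intercept, since the assumed truth has no visit effect. The visit variances can add a distortion of their own: two visits with the same 75% have a conditional odds ratio of 1.60 if their total SDs are 1 and 2. The remaining fault is that the SAP does not say which kind of odds ratio it reports.

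**Conclusion.** The point holds as a minor one. The second RANDOM statement fits a G-side visit effect that one binary answer per patient-visit, from at most 100 patients, can barely identify, and visit odds ratios can shift with it. With the estimator the code uses, the effect is negligible near 50% response; at roughly 70-85% it is typically about 1.2-fold and was up to about 1.8-fold in one set of simulated trials and 1.95-fold in the other. The larger full-likelihood shifts show how weakly the data constrain the variances. They do not forecast the reported results.

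This rests on assumed response rates, random-effect SDs and complete data; the SAP states no rates or SDs. The simulations were small and did not use SAS. Nothing here casts doubt on the descriptive proportions, and this is a secondary endpoint in an unrandomised, open-label study whose primary objective is safety.

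**What to change.** In the Section 8.6.2.1 code, do one of the following:

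1. Delete the second RANDOM statement and fit a random-intercept logistic model, preferably by quadrature with a compatible degrees-of-freedom option.
2. Replace both RANDOM statements with a marginal model: GEE, or an R-side within-patient covariance with no G-side effects.

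In either case, include Baseline Day 1 as a level of AVISITN and remove BASE as a covariate, so that each visit can be compared with Baseline; Table 1 schedules the assessment on that day. State whether the odds ratio is conditional or marginal. If the random intercept is kept, population-averaged probabilities obtained by integrating over it can be shown beside the observed percentages.

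The cost is a few lines of code. The random-intercept model allows only a simple within-patient correlation, and Kenward-Roger may have to be dropped. Ordinary GEE makes a stronger assumption about missing visits than a likelihood fit does, which matters in an 84-week study with no imputation and should be stated if that route is taken.
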